3.1 Inclusion Criteria

Participants must meet the following criteria on screening examination to be eligible to participate in the study:

1. Prior diagnosis of Langerhans Cell Histiocytosis (stratum 1) or LCH-related disorder (stratum 2) established by standard diagnostic criteria and confirmed histologically.
2. Evidence of active disease (histological confirmation of reactivation or progression is not required).
3. Performance Score > 70% (use Lansky score for age <16 and Karnofsky score for age ≥16, see Appendix I).
4. Patients of all ages will be eligible.
5. Provide signed written informed consent.

CONFIDENTIAL

This document is confidential. Do not disclose or use except as authorized.

6. In stratum 1, patients must have failed one prior systemic chemotherapy regimen. In stratum 2, RDD patients must have failed treatment with corticosteroid. EDC patients who have confirmed BRAF V600E mutations must have failed treatment with BRAF inhibitor or are not considered to be eligible for such treatment.
7. There is no limitation of amount or the type of prior therapy or drugs.
8. Female patients of childbearing potential must have a negative serum pregnancy test within 14 days prior to enrollment. Male and female patients must use an effective contraceptive method during the study and for a minimum of 6 months after study treatment.
9. Capable of understanding the investigational nature, potential risks and benefits of the study, and able to provide valid informed consent.
10. Participants must have adequate marrow functions as defined below, except those who involvement of hematopoietic system for whom these criteria can be waived:
 - Absolute neutrophil count ≥ 750 cells/ μ L
 - Platelets ≥ 750 cells/ μ L
11. Participants must have adequate organ function as defined below:
 - Total bilirubin ≤ 2.5 x institutional upper limit of normal.
 - AST (SGOT)/ALT (SGPT) < 2.5 x institutional upper limit of normal unless it is related to involvement by LCH.
 - Pediatric Population (patients < 18 years): Creatinine within normal limits or calculated creatine clearance ≥ 90 mL/min/1.73 m² as calculated by the Schwartz formula for estimated glomerular filtration rate (GFR) where GFR (mL/min/1.73 m²) = k x Height (cm)/serum creatinine (mg/dL). k is proportionally constant which varies with age and is a function of urinary creatine excretion per unit of body size; 0.45 up to 12 months of age; 0.55 children and adolescent girls; and 0.70 adolescent boys.
 - Adult Population (patients ≥ 18 years): Serum creatinine ≤ 1.0 mg/dL; if serum creatinine > 1.0 mg/dL, then the estimated glomerular filtration rate (GFR) must be > 60 mL/min/1.73 m² as calculated by the Modification of Diet in Renal Disease equation where Pediatric GFR (mL/min/1.73 m²) = $186 \times (\text{Serum Creatinine})^{-1.154} \times (\text{age in years})^{-0.203} \times (0.74 \text{ if patient is female}) \times (1.212 \text{ if patient is black})$, where serum creatinine is measured in mg/dL.
 - Alkaline phosphatase ≤ 2.5 x institutional upper limit of normal.

CONFIDENTIAL

This document is confidential. Do not disclose or use except as authorized.

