3.2 Exclusion Criteria

Participants who exhibit any of the following conditions at screening will not be eligible for admission into the study.

1. Participants who have had chemotherapy or radiotherapy within 2 weeks (6 weeks for nitrosoureas or mitomycin C) prior to entering the study or those who have not recovered from adverse events due to agents administered more than 2 weeks earlier. Corticosteroid treatment is allowed.
2. Participants may not be receiving any other investigational agents targeting Histiocytosis.
3. Clofarabine is excreted primarily by the kidneys. Therefore, drugs with known renal toxicity (e.g. vancomycin, amphotericin B, acyclovir, cyclosporin, methotrexate, tacrolimus) should be avoided to the extent possible during the 5 days of clofarabine treatment in each cycle or, if required, administered cautiously and with close monitoring.
4. Use of alternative medications (e.g., herbal or botanical that could interfere with clofarabine) is not permitted during the entire study period.
5. Uncontrolled intercurrent illness including, but not limited to ongoing or active infection, symptomatic congestive heart failure, unstable angina pectoris, cardiac arrhythmia, or psychiatric illness/social situations that would limit compliance with study requirements.
6. Pregnant women are excluded from this study because clofarabine is a nucleoside analog with the potential for teratogenic or abortifacient effects. Because there is an unknown but potential risk of adverse events in nursing infants secondary to treatment of the mother with clofarabine, breastfeeding should be discontinued if the mother is treated with clofarabine. These potential risks may also apply to other agents used in this study.
7. Individuals with a history of a different malignancy are ineligible except for the following circumstances. Individuals with a history of other malignancies are eligible if they have been disease-free for at least 5 years and are deemed by the investigator to be at low risk for recurrence of that malignancy. Individuals with the following cancers are eligible if diagnosed and treated within the past 5 years: cervical cancer in situ, and basal cell or squamous cell carcinoma of the skin.
8. Patients with a history of prior hematopoietic stem cell transplantation (HSCT), elevated conjugated serum bilirubin at study entry, uncontrolled systemic fungal, bacterial, or other infection, a history of hepatitis B or C infection or a history of cirrhosis.

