5 TREATMENT PLAN

Each patient can receive a maximum of 6 cycles of study treatment. Each treatment cycle will last 4 weeks (28 days) and a delay up to day 42 is allowed if necessary to meet eligibility criteria for starting subsequent cycles. Patients will be stratified into two groups for response analysis purposes:

Table 1: Treatment Plan for all Patients

INDUCTION			MAINTENANCE			
Cycle						
1	2		3	4	5	6
Clofarabine 25 mg/m ² /day Days 1-5 I.V. 2 hrs +/- 30 min		Disease Evaluation	Clofarabine 25 mg/m ² /day Days 1-5 I.V. 2 hrs +/- 30 min			

Induction: Clofarabine on Days 1-5 of each cycle, administered as I.V. infusion at 25 mg/m²/day. No drug treatment from Day 6 to Day 28. This cycle will be repeated once.

Evaluation of disease response (see Section 9) will be performed after 2 cycles of Induction Therapy. In the absence of disease progression, participants will be eligible to receive up to 4 cycles of Maintenance Therapy, which is identical to the Induction Therapy.

Maintenance: Clofarabine on Days 1-5 of each cycle, administered as I.V. infusion at 25 mg/m²/day. No drug treatment from Day 6 to Day 28. Cycle will be repeated for up to three more times every 28 days.

CONFIDENTIAL

This document is confidential. Do not disclose or use except as authorized.

Treatment may be administered on an outpatient basis. Expected toxicities and potential risks as well as dose modifications for clofarabine is described in Section 6. No investigational or commercial agents or therapies other than those described below may be administered with the intent to treat the participant's malignancy.

5.1 Criteria to Proceed with Cycle 1

The following assessment must be completed within 3 days prior to starting Cycle 1. **Patients need to re-meet lab eligibility criteria as described in section 3.1.**

1. Complete physical examination including height, weight and BSA.
2. Performance status $\geq 70\%$ (use Lansky score for age < 16 and Karnofsky score for age ≥ 16 , see Appendix I).
3. Concurrent medical conditions.
4. Hematology: CBC with differential and platelet count and peripheral blood smear.
5. Serum chemistries: Electrolytes (calcium, magnesium, phosphorus, sodium, potassium, chloride, and bicarbonate), blood urea nitrogen (BUN), creatinine, and serum glucose. Liver function tests (total protein/albumin, aspartate aminotransferase (AST), alanine aminotransferase (ALT), alkaline phosphatase (ALP), total bilirubin).
6. Uric Acid as clinically indicated.

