5.2 Criteria to Proceed with Subsequent Cycles

A treatment cycle will be repeated every 28 days (or no more than 42 days) if the participant does not have disease progression and any non-hematologic toxicities have recovered to grade 1 or become a tolerable grade 2, except those grade 3 toxicities specified in section 6.3.2.

The following assessment must be completed within 3 days prior to starting all subsequent cycles. **Patients need to re-meet lab eligibility criteria as described in section 3.1.**

1. Complete physical examination including height, weight and BSA.
2. Performance status $\geq 70\%$ (use Lansky score for age < 16 and Karnofsky score for age ≥ 16 , see Appendix I).
3. Hematology: CBC with differential and platelet count and peripheral blood smear.
4. Serum chemistries: Electrolytes (calcium, magnesium, phosphorus, sodium, potassium, chloride, and bicarbonate), blood urea nitrogen (BUN), creatinine, and serum glucose. Liver function tests (total protein/albumin, aspartate aminotransferase (AST), alanine aminotransferase (ALT), alkaline phosphatase (ALP), total bilirubin).

CONFIDENTIAL

This document is confidential. Do not disclose or use except as authorized.

5. Uric Acid as clinically indicated.
6. Urinalysis.
7. Concomitant Medications/Transfusions.
8. Adverse event assessment.

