6.3 Dose Modifications/Delays

6.3.1 Hematologic Toxicity

- Participants who experience prolonged neutropenia ($ANC < 500/\mu L$ for > 7 days) may receive growth factor support (see 5.3.7). If neutropenia persists ($ANC < 500/\mu L$) despite the addition of growth factor support and in the absence of hematopoietic involvement by Histiocytosis, but recovered by day 42 of the cycle, the subsequent cycle may start at a reduced dose of clofarabine by 25%. If prolonged neutropenia ($ANC < 500/\mu L$ for > 7 days) recurs in subsequent cycles after dose reduction, the participant should come off protocol treatment.
- Participants who experience prolonged thrombocytopenia (platelets $< 75,000/\mu L$ for > 7 days) in the absence of hematopoietic involvement by Histiocytosis should have their dose of clofarabine reduced by 25% in subsequent cycles. If prolonged thrombocytopenia (platelets $< 75,000/\mu L$ for > 7 days) recurs in subsequent cycles, the participant should come off protocol treatment.
- If ANC or platelets counts are not recovered by day 42 in the absence of hematopoietic involvement by Histiocytosis, the participant should be taken off study.

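### The platelet minimum in inclusion item 10 is 750/µL, the neutrophil figure and 100 times below the protocol's own thrombocytopenia threshold, so it screens out almost no one at entry or before a cycle.

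*Combined protocol and SAP*

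**What the plan says.** Section 3.1, item 10, sets two marrow criteria: an absolute neutrophil count of at least 750/µL and "Platelets ≥ 750 cells" per µL. Both can be set aside for participants with marrow disease ("except those who involvement of hematopoietic system for whom these criteria can be waived").

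The limits are used again later. Sections 5.1 and 5.2, on starting cycle 1 and later cycles, both state: "Patients need to re-meet lab eligibility criteria as described in section 3.1". The recovery condition that section 5.2 adds in its own words is confined to other organs: "any non-hematologic toxicities have recovered to grade 1 or become a tolerable grade 2".

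Section 6.3.1 handles low counts after treatment, in participants without hematopoietic involvement:
- Platelets below 75,000/µL for more than 7 days lead to a 25% dose reduction in later cycles. A recurrence ends protocol treatment.
- A separate rule takes the participant off study: "If ANC or platelets counts are not recovered by day 42". No count is given for recovery.

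Section 5 describes the permitted delay in these terms: "a delay up to day 42 is allowed if necessary to meet eligibility criteria for starting subsequent cycles".

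**The concern.** A minimum count for starting a myelosuppressive drug should not lie below the count that the same protocol treats as drug toxicity. Here the platelet minimum lies far below it and repeats the neutrophil value exactly. That suggests a copied figure or missing digits rather than a clinical choice. Nothing in the protocol explains or defends a platelet minimum of 750/µL.

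At stake is participant safety, not the operating characteristics of the design. A site that follows the text may enter a participant, or start a cycle at full dose, with a platelet count that section 6.3.1 calls thrombocytopenia if it persists. Low counts at screening are plausible from the protocol itself. Section 3.1 item 7 places no limit on prior therapy, and section 2.1 says that more than 4 or 6 courses of cladribine, a described treatment for recurrent disease, are associated with prolonged myelosuppression.

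**Working it through.** The plan derives no figure here, so there is no calculation to reproduce. The check sets the thresholds side by side in one unit and asks whether another rule supplies a platelet minimum.

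**Thresholds**

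| Cell line | Minimum to start (3.1 item 10) | Toxicity trigger, more than 7 days (6.3.1) | Minimum ÷ trigger |
|---|---|---|---|
| Neutrophils | 750/µL | 500/µL | 750 / 500 = 1.5 |
| Platelets | 750/µL | 75,000/µL | 750 / 75,000 = 0.01 |

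For neutrophils the order is coherent: the minimum sits above the trigger. For platelets it is reversed, by a factor of 75,000 / 750 = 100. Every count from 750 to 74,999/µL is below the trigger yet meets the minimum. That is (75,000 − 750) / 75,000 = 99% of the range below the trigger. This is a share of possible counts, not of participants.

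**How often the figure applies.** One check at entry plus one before each of at most 6 cycles gives 1 + 6 = 7 checks per participant.

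**Whether another rule supplies the minimum**
- *Section 5.2, own recovery rule:* non-hematologic toxicity only.
- *Section 6.3.1, dose reduction:* it needs more than 7 days below 75,000/µL and acts on later cycles, so it does not prevent a full-dose cycle 1. The weekly counts within a cycle are only recommended as clinically indicated (Table 2, footnote 4).
- *Section 6.3.1, day-42 rule:* it has no 7-day condition, but recovery is undefined. If it means a count no longer below 75,000/µL, the rule works. If it means meeting section 3.1, which section 5 supports by linking the delay to the eligibility criteria, the rule inherits 750/µL.
- *Section 3.2, exclusion 1:* it bars "those who have not recovered from adverse events due to agents administered more than 2 weeks earlier", without a number.
- *Blood counts before each cycle (5.1, 5.2):* required, but the figure they are compared with is 750/µL.

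No rule gives a numeric platelet minimum at entry or before cycle 1. For later cycles, one appears only under the first reading of the day-42 rule, and that rule does not clearly govern a start before day 42.

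**The case against.** The strongest reply has three parts.

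**The comparison.** A minimum for starting and a trigger for dose reduction are different things, and the protocol never says they must be equal; the neutrophil values also differ (750 and 500). So 100-fold measures the distance to an inferred target, not a proven error of that size. This stands as a limit on what the ratio means. It does not explain why the minimum lies below the trigger for platelets and above it for neutrophils.

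**Practical risk.** A platelet minimum of 750/µL looks implausible under a heading about adequate marrow function, so investigators would probably query it. Eligibility documents from participating sites are reviewed centrally before registration (section 4.4 and Appendix II), counts are taken within 3 days before each cycle, the investigator may stop treatment on judgement (section 5.7), and the safety committee meets quarterly (section 11.2). These protections make dosing near 750/µL unlikely. None supplies a number, however, and a reviewer checking against the written criterion would pass 1,000/µL.

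**The recovery wording.** The undefined day-42 term is a separate and conditional matter, and it is not shown that sites would read it differently. That is fair. The platelet figure needs correcting whichever reading is meant.

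**Conclusion.** The concern holds, and the figure must be corrected. The platelet minimum in item 10 is ineffective as written: 100-fold below the threshold in section 6.3.1, identical to the neutrophil minimum, and applied at up to seven checks per participant. This is an inconsistent figure in an operative safety criterion, not a miscalculation.

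The conclusion rests on the following:
- The figure is as printed in the public document. The line reads as complete, but the sponsor should check it against the master protocol.
- It concerns participants without hematopoietic involvement, since the criterion can be waived for the others.
- The value of 75,000/µL is inferred from section 6.3.1; section 3.1 does not state it.
- The number of participants affected is unknown, because the documents give no platelet distribution.

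**What to change.** 1. Correct the platelet figure in section 3.1, item 10. A minimum of 75,000/µL would match section 6.3.1; the sponsor should confirm the clinical value.
2. Add one sentence stating that the same figure defines platelet recovery for starting a cycle under section 5.2 and for the day-42 rule in section 6.3.1.
3. Carry the corrected figure to the eligibility checklist.

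The cost is one figure and one sentence in an amendment, plus the checklist. If 75,000/µL is adopted, participants without hematopoietic involvement whose counts are 750 to 74,999/µL would no longer qualify at entry or could not start a cycle until recovered. The effect on accrual and delays cannot be estimated from the documents. Sample size, the response rule (Rule A) and the toxicity rule (Rule B) stay as they are.

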3.2 Exclusion Criteria

Participants who exhibit any of the following conditions at screening will not be eligible for admission into the study.

1. Participants who have had chemotherapy or radiotherapy within 2 weeks (6 weeks for nitrosoureas or mitomycin C) prior to entering the study or those who have not recovered from adverse events due to agents administered more than 2 weeks earlier. Corticosteroid treatment is allowed.
2. Participants may not be receiving any other investigational agents targeting Histiocytosis.
3. Clofarabine is excreted primarily by the kidneys. Therefore, drugs with known renal toxicity (e.g. vancomycin, amphotericin B, acyclovir, cyclosporin, methotrexate, tacrolimus) should be avoided to the extent possible during the 5 days of clofarabine treatment in each cycle or, if required, administered cautiously and with close monitoring.
4. Use of alternative medications (e.g., herbal or botanical that could interfere with clofarabine) is not permitted during the entire study period.
5. Uncontrolled intercurrent illness including, but not limited to ongoing or active infection, symptomatic congestive heart failure, unstable angina pectoris, cardiac arrhythmia, or psychiatric illness/social situations that would limit compliance with study requirements.
6. Pregnant women are excluded from this study because clofarabine is a nucleoside analog with the potential for teratogenic or abortifacient effects. Because there is an unknown but potential risk of adverse events in nursing infants secondary to treatment of the mother with clofarabine, breastfeeding should be discontinued if the mother is treated with clofarabine. These potential risks may also apply to other agents used in this study.
7. Individuals with a history of a different malignancy are ineligible except for the following circumstances. Individuals with a history of other malignancies are eligible if they have been disease-free for at least 5 years and are deemed by the investigator to be at low risk for recurrence of that malignancy. Individuals with the following cancers are eligible if diagnosed and treated within the past 5 years: cervical cancer in situ, and basal cell or squamous cell carcinoma of the skin.
8. Patients with a history of prior hematopoietic stem cell transplantation (HSCT), elevated conjugated serum bilirubin at study entry, uncontrolled systemic fungal, bacterial, or other infection, a history of hepatitis B or C infection or a history of cirrhosis.
9. Individuals who are known to be HIV-positive on combination antiretroviral therapy are ineligible because of the potential for pharmacokinetic interactions with clofarabine. In addition, these individuals are at increased risk of lethal infections when treated with marrow-suppressive therapy. Appropriate studies will be undertaken in participants receiving combination antiretroviral therapy when indicated.

3.3 Inclusion of Women, Minorities and Other Underrepresented Populations

Individuals of both genders and all ethnic backgrounds are eligible for this study.

CONFIDENTIAL

This document is confidential. Do not disclose or use except as authorized.

4 REGISTRATION PROCEDURES

4.1 General Guidelines for DF/HCC Institutions

Institutions will register eligible participants in the Clinical Trials Management System (CTMS) OnCore. Registrations must occur prior to the initiation of protocol therapy.

An investigator will confirm eligibility criteria and will complete and sign the protocol-specific eligibility checklist.

Following registration, participants may begin protocol therapy and should begin protocol therapy within 7 days. Issues that would cause treatment delays should be discussed with the Overall Principal Investigator (PI). If a participant does not receive protocol therapy following registration, the participant's registration on the study must be canceled. Registration cancellations must be made in OnCore as soon as possible.

4.2 Registration Process for DF/HCC Institutions

DF/HCC Standard Operating Procedure for Human Subject Research titled *Subject Registration* (SOP #: REGIST-101) must be followed.

4.3 General Guidelines for Other Investigative Sites

Eligible participants will be enrolled on study centrally at the Dana-Farber Cancer Institute by the Study Coordinator (or designee). All sites should follow the procedure specified in section 4.4 to register participants prior to the initiation of protocol treatment.

Following registration, participants should begin protocol treatment within 7 days. Issues that would cause treatment delays should be discussed with the Overall PI. If a participant does not receive protocol therapy following registration, the participant's registration on the study may be canceled. The Study Coordinator should be notified of cancellations as soon as possible.

4.4 Registration Process for Other Investigative Sites

To register a participant, the following forms and source documents should be completed by the participating institution, signed, and e-mailed or faxed to the Lead Institution clinical research coordinator listed on the first page of this protocol, or faxed to [contact] (Attention: [name]):

- Signed informed consent document with patient initials and date of birth on every page of the consent
- HIPAA authorization form (if separate from the informed consent document)
- Completed Eligibility Checklist signed by the site investigator or an attending physician whose name is listed in the delegation of responsibility log sheet
- Documentation of consent and eligibility note

CONFIDENTIAL

This document is confidential. Do not disclose or use except as authorized.

- Copy of a pathology report confirming diagnosis of LCH
- All required eligibility source documents (as specified in Table 2)

The Lead Institution (DFCI) will review the submitted documents in order to verify eligibility. To complete the registration process, the Lead Institution will:

- Follow DF/HCC Standard Operating Procedure for Human Subject Research titled *Subject Registration* (SOP #: REGIST-101) and register the participant on the protocol.
- Upon receiving confirmation of registration, the Lead Institution will inform the Participating Institution and provide the study specific participant case number, and, if applicable, assigned treatment and/or dose level within 2 business days.

Treatment may not begin without confirmation from the Coordinating Center that the participant has been registered.

NOTE: Registration can only be conducted during the business hours of 8:00 AM and 5:00 PM Eastern Standard Time Monday through Friday. Same day treatment registrations will only be accepted with prior notice and discussion with the DF/HCC Lead Institution.

